2.3 Lenalidomide

Lenalidomide is the lead compound in a proprietary class of Celgene compounds known as IMiDs® with immunomodulatory and anti-angiogenic properties that could confer antitumor and antimetastatic effects. It is a derivative of thalidomide, combining higher efficacy and lower toxicity than its parent compound. Lenalidomide has been demonstrated to possess anti-angiogenic activity through inhibition of bFGF, VEGF and TNF-alpha induced endothelial cell migration, due at least in part to inhibition of Akt phosphorylation response to bFGF. In addition, lenalidomide has a variety of immunomodulatory effects. Lenalidomide stimulates T cell proliferation, and the production of IL-2, IL-10 and IFN-gamma, inhibits IL-1 beta and IL-6 and modulates IL-12 production.

Clinical experience in myelofibrosis with lenalidomide

Two similarly designed but separate phase 2 studies involving single-agent lenalidomide in a total of 68 patients with symptomatic myelofibrosis were reported in one paper. Protocol treatment consisted of oral lenalidomide at 10 mg/d (5 mg/d if baseline platelet count < 100 x 10⁹/L) for 3 to 4 months with a plan to continue treatment for either 3 or 24 additional months, in case of response. Overall response rates were 22% for anemia, 33% for splenomegaly, and 50% for thrombocytopenia. Response in anemia was deemed impressive in 8 patients whose hemoglobin level normalized from a baseline of either transfusion dependency or hemoglobin level lower than 100 g/L. Additional treatment effects in these patients included resolution of leukoerythroblastosis (4 patients), a decrease in medullary fibrosis and angiogenesis (2 patients), and del(5)(q13q33) cytogenetic remission accompanied by a reduction in JAK2(V617F) mutation burden (1 patient). Grade 3 or 4 adverse events included neutropenia (31%) and thrombocytopenia (19%). Authors concluded that lenalidomide engenders an intriguing treatment activity in a subset of patients with MF that includes an unprecedented effect on peripheral blood and bone marrow abnormalities.

To investigate the safety and efficacy of the combination of lenalidomide and prednisone in patients with MF, 40 patients were treated. Therapy consisted of lenalidomide 10 mg/d (5 mg/d if baseline platelet count < 100 x 10⁹/L) on days 1 through 21 of a 28-day cycle for six cycles, in combination with prednisone 30 mg/d orally during cycle 1, 15 mg/d during cycle 2, and 15 mg/d every other day during cycle 3. Lenalidomide therapy was continued indefinitely in patients exhibiting clinical benefit. The median follow-up was 22 months (range, 6 to 27). Responses were recorded in 12 patients (30%) and are ongoing in 10 (25%). The median time to response was 12 weeks (range, 2 to 32). According to the International Working Group for Myelofibrosis Research and Treatment consensus criteria, three patients (7.5%) had partial response and nine patients (22.5%) had clinical improvement durable for a median of 18 months (range, 3.5 to 24+). Overall response rates were 30% for anemia and 42% for splenomegaly. Moreover, 10 of 11 assessable responders who started therapy with reticulin fibrosis grade 4 experienced reductions to at least a score of 2. All eight JAK2^{V617F}-positive responders experienced a reduction of the baseline mutant allele burden, which was greater than 50% in four, including one of whom the mutation became undetectable. Grade 3 to 4 hematologic adverse events included neutropenia (58%), anemia (42%), and thrombocytopenia (13%). The combination of lenalidomide and prednisone induced durable clinical, molecular, and pathologic responses in MF.

Most frequently reported adverse events reported during clinical studies with lenalidomide in oncologic and non-oncologic indications, regardless of presumed relationship to study medication include: anemia, neutropenia, thrombocytopenia and pancytopenia, abdominal pain, nausea, vomiting and diarrhea, dehydration, rash, itching, infections, sepsis, pneumonia, UTI, Upper respiratory infection, cellulitis, atrial fibrillation, congestive heart failure, myocardial infarction, chest pain, weakness, hypotension, hypercalcemia, hyperglycemia, back pain, bone pain, generalized pain, dizziness, mental status changes, syncope, renal failure, dyspnea, pleural effusion,

pulmonary embolism, deep vein thrombosis, CVA, convulsions, dizziness, spinal cord compression, syncope, disease progression, tumor lysis syndrome, death not specified and fractures. Lenalidomide may cause breakdown products of the cancer cells to enter the blood stream, which may lead to heart rate abnormalities, kidney failure, muscle twitching, and/or muscle cramps (please refer to lenalidomide package insert or Investigator Brochure for a complete list of adverse events).

3.0 BACKGROUND DRUG INFORMATION

3.1 Ruxolitinib (INCB018424) (Refer to Investigator's Brochure)

INCB018424 phosphate, referred to herein as INCB018424, is a substituted pyrrolopyrimidine compound that acts as a potent and selective inhibitor of the Janus kinase family of enzymes. INCB018424 is a novel, potent, and selective inhibitor of the JAKs with modest selectivity for JAK2. INCB018424 potently (IC₅₀ values < 5 nM) inhibits JAKs, yet it does not significantly inhibit (<30% inhibition) a broad panel of 26 other kinases when tested at 200 nM (approximately 100 times the average IC₅₀ value for JAK enzyme inhibition). Moreover, in cell-based assays relevant to the pathogenesis of MPDs, such as JAK-STAT signaling and the growth of cytokine-dependent lines, INCB018424 demonstrated excellent potency (IC₅₀ values of 80-141 nM). This effect was not due to general cytotoxicity, because INCB018424 (up to 25 μM) had no significant effect on the growth of cytokine-independent cell lines transformed by the Bcr-Abl oncogene. In addition, INCB018424 inhibited JAK/STAT signaling and growth of a cell line expressing the JAK2 mutant variant (JAK2V617F) that has been implicated in the pathogenesis of the majority of Philadelphia chromosome negative MPD. Additional details as to the *in vitro* pharmacology of INCB018424 may be found in the Clinical Investigator's Brochure (CIB).

[figure not shown]
INCB018424 was evaluated in two mouse models where either a cytokine-dependent multiple myeloma cell line, INA-6, or a cell line, BaF3, engineered to express JAK2V617F was inoculated. The ability of INCB018424 to inhibit JAK pathway signaling as well as tumor cell survival and growth was assessed *in vivo*. *In vitro* cell biology experiments have demonstrated that the potency of INCB018424 is very similar between the cytokine-dependent INA-6 myeloma cells, with wild type JAKs, and the BaF3 cells expressing a clinically relevant mutant JAK2. As such, the *in vivo* studies described herein characterize the ability of INCB018424 to inhibit wildtype JAK2 (using the INA-6 xenograft model) and MPD-related mutant JAK2 (using a mouse model of splenomegaly driven by cells expressing the mutant JAK2V617F).

Treatment of mice with orally administered INCB018424 resulted in a dose-dependent suppression of STAT3 phosphorylation and tumor growth in the cytokine-dependent INA-6 xenograft model at doses ≥ 10 mg/kg BID. Moreover, oral administration of INCB018424 inhibited the dramatic splenomegaly in mice resulting from intravenous inoculation of the BaF3-JAK2V617F cells. Additional details as to the *in vivo* pharmacology of INCB018424 may be found in the Clinical Investigator's Brochure

(CIB). In summary, pharmacological data obtained in both *in vitro* and *in vivo* model systems support the potential utility of orally administered INCB018424 in the treatment of malignancies, including MPD such as PMF and Post-PV/ET MF.

The chemical name of INCB018424 phosphate is (*R*)-3-(4-(7*H*-pyrrolo[2,3-*d*]pyrimidin-4-yl)-1*H*-pyrazol-1-yl)-3-cyclopentylpropanenitrile phosphate (Figure 1). INCB018424 phosphate has a molecular formula of C₁₇H₂₁N₆O₄P and a molecular weight of 404.36. INCB018424 phosphate drug substance is a white to off-white powder, and is referred to herein as INCB018424.

INCB018424 Phosphate Structural Formula

INCB018424 drug product will be provided as 5 mg and 25 mg strength tablets. The tablet formulation contains the active ingredient along with commonly used excipients. All excipients are of compendial grade. The medication will be provided for free to participants in this study by the manufacturer, Incyte Inc. The 5 mg tablets are stable for six months at 40C/75% RH and at least 24 months at 25C/60% RH. The 25 mg tablets are stable for six months at 40C/75% RH and at least 36 months at 25C/60% RH.

3.2 Lenalidomide

Lenalidomide will be supplied as 5 mg capsules for oral administration. Lenalidomide will be shipped directly to the patient through the Celgene's RevAssist® program. Lenalidomide will not be provided for free to participants in this study, but will be provided upon insurance approval through commercial supply. Lenalidomide will be provided in accordance with the RevAssist® program. Per standard RevAssist® requirements all physicians who prescribe lenalidomide for research subjects enrolled into this trial, and all research subjects enrolled into this trial, must be registered in and must comply with all requirements of Celgene's RevAssist® program. Prescriptions must be filled within 7 days. Only enough lenalidomide for one cycle of therapy will be supplied to the patient each cycle.

3.3 Prednisone

Prednisone will be used from commercially available supplies.

4.0 PATIENT ELIGIBILITY CRITERIA

Inclusion criteria

1. Diagnosis of myelofibrosis (either primary or post essential thrombocythemia/polycythemia vera) requiring therapy, including those previously treated and relapsed or refractory, or if newly diagnosed, with intermediate-1 or -2 or high risk according to International Working Group (IWG) criteria.
2. Understanding and voluntary signing an IRB-approved informed consent form.
3. Age \geq 18 years at the time of signing the informed consent.
4. Disease-free of prior malignancies for \geq 2 years with exception of basal cell or squamous cell carcinoma of the skin, or carcinoma “in situ” of the cervix or breast.
5. ECOG performance status 0 to 2.
6. Patients must have adequate organ function as demonstrated by the following:
 - Direct bilirubin \leq 2.0 mg/dL
 - Serum creatinine \leq 2.0 mg/dL.
 - SGPT \leq 3 x upper limit of normal
7. Females of childbearing potential (FCBP)[†] must have a negative serum or urine pregnancy test with a sensitivity of at least 50 mIU/mL within 10 – 14 days prior to and again within 24 hours of starting lenalidomide and must either commit to continued abstinence from heterosexual intercourse or begin TWO acceptable methods of birth control, one highly effective method and one additional effective method AT THE SAME TIME, at least 4 weeks before she starts taking lenalidomide. FCBP must also agree to ongoing pregnancy testing. Men must agree to use a condom during sexual contact with a female of child bearing potential even if they have had a successful vasectomy. All patients must be counseled at a minimum of every 28 days about pregnancy precautions and risks of fetal exposure. See Appendix J: Risks of Fetal Exposure, Pregnancy Testing Guidelines and Acceptable Birth Control Methods.
8. All study participants must be registered into the mandatory RevAssist® program, and be willing and able to comply with the requirements of RevAssist®.
9. Platelets \geq 100000/uL
10. ANC \geq 1000/uL

Exclusion Criteria

1. Use of any other standard (e.g. hydroxyurea, anagrelide, growth factors) or experimental drug or therapy within 14 days or 5-half lives, whichever is longer, of starting study therapy and/or lack of recovery from all toxicity from previous therapy to grade 1 or better.
2. Known prior clinically relevant hypersensitivity reaction to thalidomide, including the development of erythema nodosum if characterized by a desquamating rash.
3. Prior therapy with lenalidomide or INCB018424.
4. Any serious medical condition, laboratory abnormality, or psychiatric illness that would prevent the subject from signing the informed consent form.
5. Suspected Pregnancy, Pregnant or lactating females.

[†] A female of childbearing potential is a sexually mature woman who: 1) has not undergone a hysterectomy or bilateral oophorectomy; or 2) has not been naturally postmenopausal for at least 24 consecutive months (i.e., has had menses at any time in the preceding 24 consecutive months).

6. Any condition, including the presence of laboratory abnormalities, which places the subject at unacceptable risk if he/she were to participate in the study or confounds the ability to interpret data from the study.
7. Known positive for HIV or infectious hepatitis, type A, B or C.
8. Known prior clinically relevant hypersensitivity to prednisone.
9. Participants with prior history of thromboembolic disease (i.e. deep venous thrombosis (DVT) or pulmonary embolism (PE) within the last six months, as Lenalidomide has demonstrated a significantly increased risk of DVT or PE.
10. Known to have a hypercoagulability syndrome (eg: antithrombin III, deficiency, anticardiolipin syndrome etc...)
11. Concurrent use of strong inducers or strong inhibitors of CYP3A4 (strong inducers are rifampin and St. John's Worth, carbamazepine, phenytoin, and barbiturates such as phenobarbital; strong inhibitors are HIV-antivirals, clarithromycin, itraconazole, ketoconazole, nefadozone, and telithromycin).
12. Incarcerated persons are excluded from the protocol.

5.0 TREATMENT PLAN

Four weeks on therapy is considered one cycle of therapy. INCB018424 and lenalidamide will be given orally in an outpatient setting. INCB018424 will be given continuously daily in 28-day cycles, and lenalidamide will be given on days 1-21 of 28 day cycles. Dosage for cycles can be reduced, increased or delayed based assessment of efficacy and on adverse events, if any occur, as described below. Delays of a maximum of 8 weeks are allowed from scheduled next cycle.

Subjects will be asked to maintain a diary to record drug administration. Subjects will be asked to bring any unused study drug to the research center at their next visit. Research personnel will count and record the number of used and unused study drug capsules/tablets (both ruxolitinib and lenalidomide) at each visit and reconcile with the subject diary. The study coordinator will question the patient regarding adherence to the dosing regimen, record the number of capsules/tablets and strengths returned in the carton, the date returned and determine treatment compliance before dispensing new medication to the study patient. Compliance below 80% will require counseling of the patient by study site personnel.

The planned dose and schedule of investigation of INCB018424 is 15 mg orally twice daily (BID), continuously in 28-day cycles. Lenalidomide will be taken orally 5 mg/day in the morning each day on days 1-21, followed by 7 days of no therapy of each 28-day cycle; medication will be mailed to participants, per the RevAssist® Program.

Twenty eight days is considered one cycle of therapy. Attempts will be made to provide an adequate treatment period of at least 6 months unless significant toxicity observed, to account for delayed time to response observed with biologic agents. Responders will continue therapy for 6 years unless progression of disease or toxicity warranting discontinuation of therapy is observed.

Prednisone will be added for patients who have not responded after 3 cycles of therapy. It will be dosed orally at the dose of 30 mg/day during cycle 4, 15 mg/day during cycle 5, and 15 mg every other day during cycle 6, and then it will be discontinued.

All patients will be registered in the Clinical Oncology Research system(CORE) at MD Anderson Cancer Center after the informed consent is signed.

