1.0 HYPOTHESIS AND OBJECTIVES

Hypothesis

Ruxolitinib (also known as INCB018424), a JAK1/2 inhibitor, and lenalidomide (immunomodulatory inhibitory drug; IMiD) are effective and tolerable treatments for patients with myelofibrosis (MF). Combination of these agents in patients with MF can improve the overall clinical response to therapy without causing excessive toxicity.

Objectives

Primary:

- to determine the efficacy of the combination of INCB018424 with lenalidomide in patients with MF, in achieving objective improvements in disease status

Secondary:

- to determine the safety of the combination in patients with MF

Exploratory:

- to explore time to response and duration of response
- to explore the effect of the combination on anemia and transfusion dependence in patients with MF
- to explore changes in JAK2V617F allele burden

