8.0 STATISTICAL CONSIDERATIONS

All subjects meeting the eligibility criteria that have signed a consent form and have begun treatment will be evaluable for response. This is a two stage, phase II trial designed to assess the effect of therapy in subjects with Primary, Post Polycythemia Vera, or Post Essential Thrombocythemia Myelofibrosis (PMF, post-PV MF, or post-ET MF). Secondary objective is to determine the safety of therapy in this population.

The primary objective of this study is to assess efficacy in terms of the objective response rate (complete and partial response, and clinical improvement by IWG-MRT) in patients with MF. The Min-Max two-stage design proposed by Simon will be implemented. Sample size and decision criteria are chosen to reduce the expected accrual if the treatment is ineffective in regard to response relative to having no interim stopping rule. The target response rate is 50%. A response rate of 35% or less will be considered unacceptable and treatment with the therapy will be discontinued. Given the response rates stated above, if the probability of inappropriately accepting a poor therapy is 10% ($\alpha=0.1$), a total sample size of 49 patients will result in 80% power ($\beta=0.2$).

In the first stage of the design, a total of 31 patients will be enrolled and the study will be put on hold to assess response. If 10 or fewer patients respond to the combination therapy, after being treated for 6 months or discontinued due to excessive toxicity or lack of efficacy, then the study will be terminated and the therapy will be declared ineffective. Those patients who stopped receiving one of the two study drugs due to safety reasons will be counted as failures in the efficacy analysis. However, if 11 or more patients respond, up to an additional 18 patients will be enrolled to complete the study.

After a total of 49 patients have been enrolled into the study, if 21 or fewer patients respond to the therapy, the therapy will be declared ineffective. However, if greater than 21 patients respond to the therapy, the therapy will be considered efficacious. The probability of early termination due to unacceptable response rate is 46% under the null hypothesis.

Data from all subjects who receive any study drug will be included in the safety analyses. Subjects who entered the study and did not take any of the study drug and had this confirmed, will not be evaluated for safety.

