The severity of the toxicities will be graded according to the NCI CTCAE v4.0 whenever possible. We will follow standard reporting guidelines for adverse events (Appendix C; Leukemia-specific Adverse Event Recording and Reporting Guidelines).

Descriptive statistics will be utilized to assess time to response and response duration.

Duration of response: duration of response is defined as the date at which the subject's objective status is first noted to be a CR, PR or CI to the date progression (no longer meeting criteria for either CR, PR or CI) is documented (if one has occurred). Patients who continue to respond as of the data cut-off date will be censored as of the date of their last assessment documenting continued response.

Time to response: The time to response is defined as the time from study registration to the first date at which the subject's objective status was classified as a response (CR, PR or CI). In subjects who do not achieve a response, time to response will be censored at the subject's last evaluation date. The distribution for each of these event-time variables (duration of response and time to response) will be estimated by Kaplan-Meier curves.

Anemia: Descriptive statistics will be used to explore improvements in anemia and transfusion dependence. The following outcomes will be summarized: mean changes in hemoglobin at monthly intervals. The proportion of transfusion independent patients not requiring transfusions on study who experience an increase of 2 g/dL in their hemoglobin relative to baseline, the proportion of transfusion dependent patients (defined as requiring a transfusion of 2 units PRBCs monthly for 3 months (12 weeks) prior to starting the trial) who become transfusion independent (not requiring a transfusion of PRBCs over a period of 3 months (12 weeks) while on study), the proportion of transfusion dependent patients who become transfusion independent and have a 1 g/dL increase in hemoglobin relative to baseline, and the proportion of transfusion independent patients requiring a transfusion while on study.

JAK2V617F Allele burden: Change in JAK2V617 allele burden from baseline to each visit where it is measured.

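### The response count in Section 8 includes responses that begin after protocol-added prednisone, so a positive result supports the strategy with prednisone and cannot by itself be credited to ruxolitinib plus lenalidomide.

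*Combined protocol and SAP*

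**What the plan says.** All references are to the combined protocol and SAP.

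- **Objective (Section 1.0).** The primary aim is "to determine the efficacy of the combination of INCB018424 with lenalidomide in patients with MF". Prednisone is not named.
- **Treatment (Section 5.0).** "Prednisone will be added for patients who have not responded after 3 cycles of therapy". The dose is 30 mg/day in cycle 4, 15 mg/day in cycle 5 and 15 mg on alternate days in cycle 6, after which it stops.
- **Endpoint (Sections 6.0 and 8.0).** Response is CR, PR or clinical improvement (CI), taken as best overall response. A CI must last at least 8 weeks to be validated.
- **Stage 1 rule (Section 8.0).** "If 10 or fewer patients respond to the combination therapy, after being treated for 6 months", or after stopping early for toxicity or lack of efficacy, the trial ends.
- **Final rule (Section 8.0).** With 49 patients, "if greater than 21 patients respond to the therapy, the therapy will be considered efficacious". No time window is given here.
- **Changes in treatment (Section 8.0).** "Those patients who stopped receiving one of the two study drugs due to safety reasons will be counted as failures in the efficacy analysis". Nothing is said about patients who gain a third drug.
- **Time to response (Section 8.0).** "The time to response is defined as the time from study registration to the first date" of response, summarised by Kaplan-Meier.

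**The concern.** Prednisone goes only to patients who have not responded to the two drugs by the end of cycle 3. Any response first noted in cycles 4 to 6 in such a patient arises on three drugs, yet it enters the same count as a response on two. The stage 1 wording then calls that count response to the combination therapy.

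A prednisone contribution is plausible. Section 2.3 gives anaemia and spleen response rates of 22% and 33% with lenalidomide alone, and 30% and 42% with lenalidomide plus prednisone. These come from different studies, so they show plausibility and nothing about size.

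What is at stake is the wording of the conclusion. A result of 22/49 or more would naturally be reported as efficacy of ruxolitinib plus lenalidomide, and no planned table would show how many of those responses began before prednisone.

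**Working it through.** **1. Reproduce the design.** Inputs from Section 8.0: n1 = 31, stop if 10 or fewer respond; N = 49, ineffective if 21 or fewer respond; unacceptable rate 35%; target rate 50%. For a true overall response rate p:

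- P(early stop) = P[Bin(31, p) ≤ 10]
- P(declare efficacy) = Σ over x = 11 to 31 of P[Bin(31, p) = x] × P[Bin(18, p) ≥ 22 − x]

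| Quantity | Exact | Stated |
|---|---|---|
| Type I error, p = 0.35 | 0.097 | 0.10 (limit) |
| Power, p = 0.50 | 0.801 | 80% |
| Early stop, p = 0.35 | 0.455 | 46% |

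The plan's figures are correct. A search for the smallest N that meets both error limits returns the same design: 10/31, then 21/49.

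**2. Identify which rate p is.** The count is best overall response with no cut-off at the start of prednisone, and 6 months covers cycles 4 to 6. So p is the response rate of the whole strategy. The error rates in step 1 belong to that rate and not to the two-drug rate.

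**3. Illustrate the gap.** Let the two-drug rate be 35%, with all two-drug responses beginning before prednisone. Let a share q of all remaining patients, including those who never reach cycle 4, respond after prednisone. Then p = 0.35 + 0.65q.

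| q (assumed) | p | P(early stop) | P(declare efficacy) |
|---|---|---|---|
| 0 | 0.3500 | 0.455 | 0.097 |
| 5% | 0.3825 | 0.312 | 0.206 |
| 10% | 0.4150 | 0.195 | 0.362 |
| 15% | 0.4475 | 0.111 | 0.543 |

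The documents give no value for q.

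**4. Check whether the planned Kaplan-Meier curve closes the gap.** Section 5.6 schedules response assessment each month for three cycles and then every 3 to 6 cycles. For a patient on schedule, cycle 4 starts at 3 × 4 = 12 weeks, so the week-12 value is close to the pre-prednisone rate. But the curve runs from registration and not to each patient's first prednisone dose. One permitted 8-week delay moves the start of cycle 4 to 12 + 8 = 20 weeks. The curve therefore shows the split approximately.

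**The case against.** **Prednisone is openly part of protocol therapy.** It has its own drug section (3.3), an exclusion criterion (Section 4.0) and a fixed trigger, dose and stop, and the final rule judges the therapy as a whole. This stands, and it is why the decision rules need no change. It does not settle attribution, because Sections 1.0 and 8.0 still speak of the combination.

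**A late response may be due to the two drugs.** This also stands. Section 5.0 asks for at least 6 months of treatment because responses may be delayed. The lenalidomide-prednisone study in Section 2.3 had a median time to response of 12 weeks (range 2 to 32). Section 5.1 allows dose escalation for sub-optimal benefit, which may coincide with prednisone. A single arm cannot separate these causes.

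Three stronger readings are therefore tempting but unsupported:

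- *A pre-prednisone rate under 35% means the two drugs failed.* The protocol does say "A response rate of 35% or less will be considered unacceptable", but for its own response rule, which at stage 1 means 6 months. It sets no threshold for a count at about 3 months.
- *Fewer than 22 pre-prednisone responders in a positive trial shows that prednisone carried the result.* The same pattern arises with no prednisone effect. Take a two-drug rate of 50%, and assume 90%, 80% or 70% of responses are first noted before cycle 4. Then 30%, 64% or 88% of positive trials would have fewer than 22 such responders.
- *The pre-prednisone rate is a lower limit for the two drugs.* This is not assured. A CI first noted before prednisone may complete its 8 weeks on three drugs.

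**The split can be derived afterwards.** It can, since the dates exist. But reporting it would then be optional and decided with the results in view.

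**Conclusion.** The point holds as a matter of attribution and reporting. The 11/31 and 22/49 rules are valid for the strategy that includes prednisone, with type I error 0.097 and power 0.801. As written, they cannot by themselves credit a positive result to ruxolitinib plus lenalidomide.

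The size of the gap is unknown. The figures of 21%, 36% and 54% rest on an assumed two-drug rate of 35%, on all two-drug responses beginning before cycle 4, and on assumed shares of 5%, 10% and 15% responding after prednisone. They show how sensitive the conclusion is; they do not estimate a prednisone effect. A reader might also infer that the sample size or error rates are wrong, but they reproduce exactly. This is a cheap improvement in what the trial can conclude and not a flaw in its validity.

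**What to change.** Add to Section 8.0:

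> The 11/31 and 22/49 rules apply to the treatment strategy including protocol prednisone, and conclusions will be worded accordingly. Responders will be reported, with exact 95% CIs, as first noted before prednisone (or never given prednisone) or first noted after the first prednisone dose, at stage 1 and at the end. For the first group, the number given prednisone before the 8-week CI validation was complete will also be reported. Responses first noted after prednisone will not be attributed to the two drugs alone.

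**Cost.** This needs text in Section 8.0 and one derived flag. The response date is already required, since duration of response starts when "objective status is first noted to be a CR, PR or CI". Section 5.3 captures medications in the CRF, and Section 5.1 requires prednisone changes to be documented. No patients, visits or assessments are added, and the sample size, both bounds and the prednisone rule are unchanged.

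**Downside.** The pre-prednisone rate is descriptive, covers about 3 months and misses late two-drug responses. The added text does not alter the probabilities in the illustration; it makes the two parts of the count visible.
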